Theoretical underpinnings of Resourcefulness Training posit that caregivers with greater resourcefulness will experience less stress and, as a result, will augment their caregiving capacity. This intervention involves the following components: 1) a face-to-face session for teaching social (help-seeking) and personal (self-help) resourcefulness skills **using a 32 minute video**, 2) ongoing access to video vignettes of parents of technology-dependent children describing the application of resourcefulness skills in daily life, 3) 4 weeks of skills' reinforcement using daily journal writing by the parents, and 4) weekly phone calls from the intervention nurse over 4 weeks after face-to-face intervention training. Booster sessions for the intervention group at 2 and 4 months post-intervention consist of a phone call and one week of journal writing. The Attention Control group will receive weekly phone calls for the first four weeks plus any usual care. In this exploratory stage of intervention work, we will evaluate the impact of the intervention on psychological and physical outcomes and family outcomes (family functioning) over time and whether changes in resourcefulness skills mediate these outcomes.

The specific aims of the study are to: Aim 1: Determine whether Resourcefulness Training versus Attention Control improves psychological (general mental health, depressive cognitions, depressive symptoms, appraised stress, burden) and physical outcomes (general physical health, chronic stress [hair cortisol]) and family outcomes (family functioning) over 6 months in parents of technology dependent children, after controlling for the parents' race/ethnicity, sex, family income, and children's functional status. Aim 2: Determine whether changes in psychological and physical outcomes and family outcomes are mediated by changes in parents' levels of resourcefulness (personal and social).

Background

1. Describe the relevant prior experience and gaps in current knowledge describing how it will add to existing knowledge.
2. Describe any relevant preliminary data.

Please add relevant references at the end of the protocol, not at the end of this section.

Introduction/Background

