Research Design. A quasi-experimental RCT design with random assignment will be used to test the efficacy of a Resourcefulness Training (RT) intervention compared with an attention control group in mothers and fathers of technology-dependent children. All participants will receive a face-to-face visit from study staff for the T1 data collection. In addition, the intervention group will receive individually tailored RT web based instruction via an approximately 30 minute video that provides details on each of the 8 resourcefulness skills with short examples of application, instruction on journal writing to practice and reinforce use of resourcefulness skills, access to video tapes of parents describing application of resourcefulness skills in the care of their technology-dependent child. Parents will be asked to provide their email address so that we may send them invitation for access to the website that they may visit at any time to access the video tapes. Data will also be collected face-to-face at 3 months (T3) and 6 months (T4) post-intervention. At 6 weeks parents will be emailed a link to the REDCap survey for Time 2 data collection and contacted by phone for SF-12 survey with email reminders. Open-ended questions following their final data collection appointment will allow mothers/fathers to discuss feasibility, acceptability, and fidelity of this intervention and suggestions for potential modification of the intervention and follow up procedures. For this study, 99 female participants and 24 male participants are expected to be enrolled that takes into account 10% attrition.

Measures/Instruments.

The **Depressive Cognition Scale** an 8-item scale ($\alpha = .75$), will measure depressive thought patterns that may lead to depression.⁸ Responses on a 6-point scale range from strongly agree (5) to strongly disagree (0) with a score range 0-40. Items include depressive cognitions such as hopelessness and worthlessness; higher scores indicate more depressive cognitions.

The **Resourcefulness Scale**, a 28-item scale ($\alpha = .85$), will assess both personal (16 items) and social (12 items) resourcefulness.⁹ Responses on a 6-point scale range from extremely descriptive (5) to not descriptive (0) with a score range 0-140; higher scores indicate greater resourcefulness. Construct validity was assessed using confirmatory factor analysis.

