each outcome over time using different residual covariance structures and select the most appropriate structure using likelihood-based criteria. Fixed effects will include a continuous variable to represent time since randomization, an indicator variable to represent the intervention, and stratification factors used during randomization (facility, OTA technology group, sex and race/ethnicity). Assuming a linear rate of change over time, the regression coefficient of the terms representing interactions between time and the intervention indicator variable will be used to estimate the difference in the monthly rate of change in each outcome between the two arms.

To determine if resourcefulness mediates the effect of the resourcefulness intervention on parent outcomes, a model-based causal mediation model^{110,111} will be fit using separate generalized linear models of parent outcomes at 3 months after randomization that adjust for the intervention indicator variable, stratification factors, and the mediator at 6 weeks after randomization. This model will allow us to decompose the total effect of the resourcefulness intervention on maternal outcomes at 3 months into direct and indirect (or mediated) effects and will allow us to estimate the proportion of the total effect that is mediated. Variance estimates, and consequently 95% confidence intervals, will be estimated using a bootstrapping procedure based on 1000 bootstrap samples. To more fully explore the temporal pattern of mediated effects, we will use similar models to also estimate the mediated effect using measurements of the mediator and maternal outcome taken at other time points as well (e.g., total effect of resourcefulness intervention on parent outcomes at 6 months that are mediated by personal or social resourcefulness at 3 months).

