To account for any multiple comparisons, a Bonferroni-corrected two-sided significance level will be applied to all analyses for all aims. Additionally, as with any study, we expect some level of missing data at each time point. To adjust for the missing data in all mixed-models analyses, we will use pattern-mixture models. This modeling approach will be applied to each model to ensure that missing data is adequately accounted for in each analysis. In contrast to a “completers only” approach, pattern-mixture models will provide a consistent and asymptotically efficient estimate of the effect of intervention on the monthly rate of change in parent and family outcomes when data is missing not at random.

Secondary Analyses. To obtain more precise estimates of the intervention effect on the time point interval rate of change in each parent or family outcome, additional multivariable analyses will characterize and estimate the relationship between potential covariates at baseline and each outcome. For continuous variables that do not have a linear relationship with the outcome, appropriate transformations or categorization will be considered. For nominal and ordinal variables, the number and type of categories will be considered to obtain

the optimum relationship, if any, with the outcome. Based on a two-sided significance level of 0.15, any baseline covariate found to be associated with the outcome will be included in the model described for the Primary Analyses.

Modification of the intervention effect on the monthly rate of change in each parent outcome will also be tested in each model by including an interaction between a pre-specified effect modifier measured at baseline, the intervention indicator variables, and the variable representing time since randomization. Should an interaction be detected based on a two-sided significance level of 0.05, the monthly rate of change in each outcome will be estimated in each of the arms for each level of a categorical effect modifier or at the 25th, 50th, and 75th percentiles of a modifier that is measured on an interval scale.

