Sensitivity analyses will also be applied to all mediation models described for the Primary Analysis to evaluate the assumption of sequential ignorability (e.g., no unmeasured confounders of the association between the mediator and each maternal outcome). As described by Imai et al,¹¹¹ this analysis will assess how large an effect an unobserved confounder must have on both models to cause a non-significant mediated effect.

Confidentiality of Specimens and Banking

I am not storing specimens in this research project – *please leave the rest of this section blank*

Describe:

- The source of the specimens* **Hair samples for cortisol level**
- Where the specimens will be stored* **Locked file cabinet in study office**
- How long the specimens will be stored* **Until final data collection then shipped together in one batch to lab for analysis**
- How the specimens will be labeled* **Each hair sample will be labeled with participant ID number and time point sample taken**
- How the specimens will be accessed* **Going into locked file cabinet**
- Who will have access to the specimens* **Members of the research team who have IRB approval.**
- When and how will the specimens be destroyed* **The specimens will be autoclaved and destroyed following processing by the lab.**
- How will the specimens be transported (Please note if transporting specimens, a Material Transfer Agreement (MTA) is required).* **The hair samples are wrapped in foil and enclosed in an envelope. All samples will be shipped next day air FedEx to the lab in a box.**

Describe:

- The procedures to release specimens including:*
 - i. *The process to request a release*

- ii. *Approvals required for a release*
- iii. *Who can obtain specimens*
- iv. *The data to be provided with specimens, including if the data will be identifiable to others* **No data other than ID number and time point.**

For genomic data, please include an attestation of no master list and no attempt will be made to re-identify the specimens.

Are you storing the specimen for future use for other research projects?

- Yes
- No

Confidentiality of Data

1. To maintain the confidentiality of the data:
 - I will use a unique study identifier (not derived from the participants personal identifiers) to code individuals' data and I will store this ID log separate from study data.
 - Other (please explain)

2. How are you storing your electronic data?
 - UH Redcap
 - CWRU Redcap
 - Secure Research Environment (SRE)
 - CWRU Box

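### The Bonferroni rule states no base alpha, family or number of tests; Holm on a stated family gives the same error control and never rejects fewer hypotheses

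*Combined protocol and SAP*

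**What the plan says.** The rule closes the Primary Analyses part of the Data Analysis Plan, which covers Aims 1 and 2: "a Bonferroni-corrected two-sided significance level will be applied to all analyses for all aims". Neither that section nor any other states a base significance level, a divisor or a list of the tests covered, and no single outcome is named as primary.

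The material for a count is elsewhere.

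- **Aim 1 (Objectives)** lists five psychological outcomes, two physical outcomes and family functioning. Primary Analyses tests the parent outcomes by a time-by-arm interaction.
- **Aim 2 (Objectives)** is to "Determine whether changes in psychological and physical outcomes and family outcomes are mediated by changes" in personal and social resourcefulness. The main mediation model takes the mediator at 6 weeks and the outcome at 3 months.
- **Other lags.** As further exploration of timing, "we will use similar models to also estimate the mediated effect using measurements of the mediator and maternal outcome taken at other time points". The example given is 3 months to 6 months.
- **Mediation intervals.** "Variance estimates, and consequently 95% confidence intervals, will be estimated using a bootstrapping procedure based on 1000 bootstrap samples".
- **Mediation sensitivity analysis** asks "how large an effect an unobserved confounder must have on both models to cause a non-significant mediated effect", without saying at what level significance is judged.
- **Secondary Analyses**, under its own heading: "Modification of the intervention effect on the monthly rate of change in each parent outcome will also be tested in each model", with the criterion "Should an interaction be detected based on a two-sided significance level of 0.05".

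On size, Research Design says that "99 female participants and 24 male participants are expected to be enrolled that takes into account 10% attrition", while the Purpose statement speaks of 94 parents.

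**The concern.** A Bonferroni level cannot be computed without a divisor and a starting alpha, and the plan gives neither. The words point to a family across both aims, but an analyst could equally defend a separate family for Aim 1. The two readings set thresholds that differ threefold (0.00625 against 0.0021). If the choice is left until results are known, an outcome with p = 0.004 passes or fails according to a decision made after it was seen.

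The method is a separate matter. Once the family is fixed, Bonferroni is never better than Holm at deciding which hypotheses to reject. With eight outcomes, no designated primary and roughly 94 to 111 analysable parents, power is scarce enough that a free gain is worth taking, even a small one.

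**Working it through.** **Inputs.** Outcomes: 5 + 2 + 1 = 8 (Objectives, Aim 1). Mediators: 2 (Aim 2), so 8 × 2 = 16 mediated effects at the main lag. N: 123 × 0.9 = 110.7, taken as 111 (Research Design), and 94 (Purpose). The plan states no power or alpha calculation, so it has no figure of its own to reproduce. My assumptions are a base alpha of 0.05 two-sided, equal arms, an effect of 0.5 SD (the plan anticipates a medium effect and gives no number), correlation 0.5 between test statistics, and a simple two-arm z-test in place of the mixed-model slope test, whose variance components are not given.

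**Thresholds.**
- Aim 1 only: 0.05/8 = 0.00625.
- Both aims at the main lag: 8 + 16 = 24, and 0.05/24 = 0.0021.
- Only if a second, exploratory lag is also counted: 24 + 16 = 40, and 0.05/40 = 0.00125.

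**Bonferroni power per true effect** = Φ(0.5 × √N/2 − z), where z is the two-sided critical value. The mean is 0.5 × √111/2 = 2.634 or 0.5 × √94/2 = 2.424.
- 8 tests, z = 2.734: Φ(−0.100) = 46% at N=111; Φ(−0.310) = 38% at N=94.
- 24 tests, z = 3.078: Φ(−0.444) = 33%; Φ(−0.654) = 26%.

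**Why Holm cannot do worse.** Holm compares the ordered p-values with 0.05/m, 0.05/(m−1), and so on up to 0.05. Every threshold is at least 0.05/m, so any p-value that passes Bonferroni, and all smaller ones, pass Holm. Its family-wise error stays at or below 5% under any dependence: with m₀ true nulls, the first false rejection needs a true-null p-value at or below 0.05/m₀, and the probabilities of that sum to at most 0.05.

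**Size of the gain**, by simulation (200,000 sets of correlated z-statistics per row), mean power per true effect:

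| Tests | Real effects | N=111 Bonferroni | N=111 Holm | N=94 Bonferroni | N=94 Holm |
|---|---|---|---|---|---|
| 8 | 1 | 46% | 46% | 38% | 38% |
| 8 | 2 | 46% | 47% | 38% | 39% |
| 8 | 4 | 46% | 49% | 38% | 40% |
| 8 | 8 | 46% | 56% | 38% | 46–47% |
| 24 | 8 | 33% | 34% | 26% | 27% |

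No Bonferroni rejection was missed by Holm. With all eight nulls true, the family-wise error was 4.0% for both. The chance of finding at least one true effect is practically unchanged (about 86% for both at N=111 with eight real), because Holm's first step is the Bonferroni test.

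**Other effect sizes**, 8 tests, all real, N=111: 12% to 15% at 0.3 SD, 27% to 33% at 0.4 SD, 66% to 78% at 0.6 SD. With four real at 0.3 SD: 12% to 13%.

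**The case against.** **Holm is a matter of taste, and the headline gain is a best case.** Much of this stands. Bonferroni is valid, and Holm needs the same fixed family, so it does not by itself cure the missing divisor. A reader might infer from 46% to 56% that Holm restores most of the lost power. It does not. That figure needs the narrow eight-test family with every outcome affected. Even then it recovers 10 of the 29 points between the unadjusted 75% and 46%. On the 24-test family, which is closer to the plan's wording, the gain is about one point. What remains is that Holm costs nothing in error control.

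**The plan may seem to contradict itself by testing interactions at 0.05.** A reader might infer this from the word all in the rule. The documents do not support it firmly. The rule closes Primary Analyses for the two aims. Effect modification comes under a separate Secondary Analyses heading, belongs to neither aim, and at 0.05 only triggers estimation within levels of the modifier. The chance of at least one false interaction, 1 − 0.95⁷ = 30% for seven independent outcomes or 1 − 0.95⁸ = 34% for eight, would matter only if those tests were reported as covered by the rule. One clause settles it.

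**The 95% mediation intervals may seem to show that Aim 2 escapes correction.** They do not. Such intervals can sit beside a corrected test, and the reference to non-significance in the sensitivity analysis is compatible with a corrected level. The plan simply does not say how mediation is judged.

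**The threshold may seem to vary fivefold.** That needs 0.00125, which counts models that the plan presents as further exploration. The firmer range is 0.00625 to 0.0021.

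**Conclusion.** The concern holds in a limited form. The plan commits to a corrected level that cannot be computed from what it says: base alpha, family and size are all missing, and two reasonable readings give Aim 1 thresholds of 0.00625 and 0.0021. At N=111 and the assumed 0.5 SD, that choice alone moves Bonferroni power per outcome between 46% and 33%, which is more than the change from Bonferroni to Holm in any case examined.

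Holm is the better rule on whichever family is chosen. Its advantage in rejections is a mathematical fact. Its size is not: 0 to 10 points with eight tests at N=111, and about 1 point with 24 tests of which eight are real. These sizes rest on equal effects across outcomes, correlation 0.5 and a two-arm test standing in for the slope test. Hair cortisol, which Table 1 does not schedule at 6 weeks, may depart from the equal-effects assumption. The documents do not show a contradiction over the interaction tests, nor an uncorrected decision rule for mediation.

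**What to change.** Before outcomes are compared by arm, replace the Bonferroni sentence with wording to this effect:

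1. Holm's procedure at a two-sided family-wise level of 0.05.
2. The family is the combined 24 tests: eight time-by-arm tests (Aim 1) and sixteen outcome-by-mediator effects at the 6-week to 3-month lag (Aim 2). This keeps the plan's own promise of control across the aims. If the sponsor prefers control per aim (families of 8 and 16), the plan should say that cross-aim control is given up, since error across both aims can then approach 0.05 + 0.05 = 10%.
3. The 95% mediation intervals are unadjusted and descriptive. Mediation is judged by Holm-adjusted bootstrap p-values, with the p-value defined. If it is based on the estimate and its bootstrap standard error, the planned 1000 samples can serve. If it is based on percentiles, 1000 samples give steps of about 2/1000 = 0.002, too coarse against a first threshold of 0.0021, and more samples are needed.
4. One clause: the other mediation lags and the 0.05 effect-modification tests are exploratory and outside the rule.

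**Cost.** Wording only, with no new data or participants. Holm has no simple matching simultaneous intervals, so unadjusted intervals will stand beside adjusted p-values, and the two can appear to disagree. The combined family also lowers Aim 1 power: at N=111 with all eight outcomes affected and no true mediation, 34% under Holm on 24 against 56% under Holm on 8. Mediation judged at a corrected level will have less power than the 95% intervals suggest, but the plan's existing promise already implies that.

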The **CES-D Scale** will measure depressive symptoms.¹⁰ The 20-item interval scale ($\alpha = .85$), with responses ranging from rarely (0) to most or all of the time (3) is summed; higher scores indicate more depressive symptoms. A cut-off of 16 is used to identify those at high risk for clinical depression.

Medical Outcomes Short Form Health Survey (SF-12 v.2) is a 12-item scale that is a measure of perceived physical health status and mental health. It measures the following eight concepts: physical function, general health, bodily pain, role limitation due to physical health, bodily pain, vitality, social function, role limitation due to emotional problems and mental health. Two distinct component scores (physical, mental) are then derived. Median α for the two subscales is $> .76$.²⁷

The **Feetham Family Functioning Survey (FFFS)**, a 25-item scale ($\alpha = .85$), will assess family functioning.¹² Responses on a 7-point likert scale range from little (1) to much (7) that asks (a) how much is there now? (b) how much should there be? This provides a discrepancy score; higher scores reflect greater the dissatisfaction with family functioning.¹²

The **Demographic Characteristics Questionnaire** includes questions about the child's age, mother's/father's age, education and race. Questions regarding additional covariates such as caregiving duration (years), home health care nursing hours per week and family income are also included. Mothers/fathers will also be asked if they are willing to be contacted in at a later date should future studies be conducted. If yes, mothers/fathers will complete the section of the demographic questionnaire with address, zip codes and names and contact information of 2 persons who might know whereabouts should they move.

The **Functional Status II-Revised (FSII-R)** will assess the child's functional status.¹³ The 14-item tool ($\alpha = .86$) is administered in two parts. Part 1 asks parents about performance of the activity or behavior in the past two weeks with responses ranging from never/rarely (0) to almost always (2); Part 2 probes responses indicating poor function to determine if responses were due to illness. Higher scores indicate higher function.¹³

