After confirming the child's assent and obtaining the participant's written informed consent, the participant will be assigned a code number. Mothers/fathers will be randomly assigned to one of two treatment conditions- Resourcefulness Training intervention or Attention Control using the Minim computerized method of random assignment based on parent gender, child's type of technology (mechanical ventilation or intravenous medication/nutrition, all others), race ethnicity (White non-Hispanic, all others). Data collection will take place in a private place of the mother's/father's choosing such as her/his home. The instruments should take about 50 minutes to complete at initial enrollment but thereafter it should take about 30 minutes (Table 1). After the participant has completed the self administered questionnaires, the interviewer will score the CES-D. If the total score of the CES-D exceeds the cutoff of 16 for depressive symptoms the participant will be notified and the information regarding mental health resources will be given-(see additional files). Following T1 data collection, mothers/fathers will receive either intervention or attention control protocol according to their random assignment. The RT intervention which includes instruction on maintaining a 28 day journal will take about 45-50 minutes to review with participants. At T4, one additional questionnaire, Resourcefulness Skills Scale, will be given to the Resourcefulness Training intervention group only to assess for intervention fidelity. Reminder post cards will be sent as needed. A \$25 gift card will be given following completion of questionnaires at each of four time points. Following completion and submission of all questionnaires and the RT journals, participants will be interviewed via speaker phone to determine the feasibility, acceptability and fidelity of the intervention. Telephone interviews will take place at a time convenient for the participant and will be audio-recorded. In order to aid in retention, participants will be mailed birthday cards on the parent's and child's birthdays as well as monthly postcards with an inspirational message and contact information for the study office. The **RT intervention** group will be taught RT skills and mnemonic strategies (acronyms, practice) to facilitate recall of RT skills using a web based program that includes a video approximately 32 minutes long. The 8 letters in the acronym **RESOURCE** will be used to prompt recall: **R**ely on family/friends; **E**xchange ideas with others; **S**eek professionals or experts; **O**rganize daily activities; **U**se positive self-talk; **R**eframe the situation positively; **C**hange from usual reaction; **E**xplore new ideas. Practice of RT will occur through using a personal semi-structured journal (example in other study documents) to daily record which resourcefulness skills were used that day as well as one's thoughts and feelings related to specific situations in which the resourcefulness skills were used. As intervention reminder tools mothers/fathers will be given a laminated card to keep in their journal as well as a magnet to

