answer the interview and study questions. Parents will be told that they may choose to take a break at any point during the interview. The amount of time required for participation in the study may also be viewed as an inconvenience. A potential emotional risk during the interview is that recalling information regarding their child’s course of illness and home management difficulties may make some parents uncomfortable. Participants will be told that they may withdraw from the study at any time. The interviewer will be vigilant to assess the participant’s discomfort. Participants experiencing considerable discomfort will be asked if they wish to stop the interview and will be given supportive assistance by the interviewer. The mother/father will then be given the number of United Way First Call (211) to access on call mental health professional services in their local area or Cuyahoga County 24-Hour Mental Health Crisis Information and Referral [contact]). If any participant is noted to have a level of depressive symptoms above the recognized cutoff of 16 on the Center for Epidemiological Studies (CES-D) measure she/he will be told of the findings and given an information sheet regarding accessing mental health care resources such as United Way First Help (phone 211) or the Cuyahoga County 24-Hour Mental Health Crisis Information and Referral [contact]). Any participant noted to have a score of 23 or above on the CES-D will be assessed for imminent risk of suicide by asking if they have had any thoughts of harming themselves in any way or perhaps killing themselves. If the answer to any portion of the question is “yes” the participant will be told of a concern for their safety and the necessity for the interviewer to contact the Mobile Crisis Team from the Cuyahoga County 24-Hour Mental Health Crisis, Information and Referral Hotline immediately. The risks and discomforts involved are reasonable because the risks are temporary and can be minimized by the above procedures. In addition, the discomfort is no more than what the participant might experience in her/his daily life.

**3. Describe: Procedures to decrease risk- See above
Drugs/Devices; Source Records- Not Applicable**

- Procedures performed to lessen the probability or magnitude of risks*

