Minimal risk is involved with participation in this study. Physical discomforts might involve fatigue due to the length of time (about 50 minutes) needed to answer the interview and study questions. Parents will be told that they may choose to take a break at any point during the interview. The amount of time required for participation in the study may also be viewed as an inconvenience. A potential emotional risk during the interview is that recalling information regarding their child’s course of illness and home management difficulties may make some parents uncomfortable. Participants will be told that they may withdraw from the study at any time. The interviewer will be vigilant to assess the participant’s discomfort. Participants experiencing considerable discomfort will be asked if they wish to stop the interview and will be given supportive assistance by the interviewer. The mother/father will then be given the number of United Way First Call (211) to access on call mental health professional services in their local area or Cuyahoga County 24-Hour Mental Health Crisis Information and Referral [contact]). If any participant is noted to have a level of depressive symptoms above the recognized cutoff of 16 on the Center for Epidemiological Studies (CES-D) measure she/he will be told of the findings and given an information sheet regarding accessing mental health care resources such as United Way First Help (phone 211) or the Cuyahoga County 24-Hour Mental Health Crisis Information and Referral [contact]).

Any participant noted to have a score of 23 or above on the CES-D will be assessed for imminent risk of suicide by asking if they have had any thoughts of harming themselves in any way or perhaps killing themselves. If the answer to any portion of the question is “yes” the participant will be told of a concern for their safety and the necessity for the interviewer to contact the Mobile Crisis Team from the Cuyahoga County 24-Hour Mental Health Crisis, Information and Referral Hotline immediately. The risks and discomforts involved are reasonable because the risks are temporary and can be minimized by the above procedures. In addition, the discomfort is no more than what the participant might experience in her/his daily life.

2. *If applicable, indicate which experimental procedures may have risks to the research participants that are currently unforeseeable.*

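### A parent who stops a face-to-face session in distress before a CES-D score exists need not be asked the self-harm question

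*Combined protocol and SAP*

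**What the plan says.** The distress procedure appears in the same terms in Study Design, Procedures and Timeline (item 2) and in Risks to Research Participants (item 1). The interviewer is to watch for discomfort, and breaks are allowed at any point. Then: "Participants experiencing considerable discomfort will be asked if they wish to stop the interview and will be given supportive assistance by the interviewer". Next: "The mother/father will then be given the number of United Way First Call", with a county 24-hour crisis line as the alternative.

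The self-harm question stands apart from that procedure and depends on a score: "Any participant noted to have a score of 23 or above on the CES-D will be assessed for imminent risk of suicide". A positive answer to any part of it obliges the interviewer to contact the Mobile Crisis Team at once. A lower step, for scores above 16, gives notification and a resource sheet.

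The procedures text in Study Design, Procedures and Timeline says when the score is produced: "After the participant has completed the self administered questionnaires, the interviewer will score the CES-D". Measures/Instruments describes the CES-D as a 20-item scale "with responses ranging from rarely (0) to most or all of the time (3) is summed".

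T1 is a face-to-face visit, and Research Design adds: "Data will also be collected face-to-face at 3 months (T3) and 6 months (T4) post-intervention". T2 is remote: "At 6 weeks parents will be emailed a link to the REDCap survey for Time 2 data collection".

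**The concern.** The plan foresees that recalling the child's illness and home care may upset some parents, and it tells the interviewer to look out for this. It also treats possible self-harm as serious enough for an immediate crisis call. The two safeguards are not connected. Visible distress leads to an offer to stop and a telephone number; only a score leads to the question. A parent too upset to finish can thus receive less assessment than a calmer parent who finishes and scores 23.

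What is at stake is participant safety. A crisis number relies on the distressed parent to act, whereas the pathway at 23 or above makes the interviewer act.

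**Working it through.** The plan gives no figure to reproduce. The check is to trace the procedure, look for any other provision that would close the gap, and do a little arithmetic on the scale.

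**1. Tracing the stated steps.** Considerable discomfort → session stopped → questionnaires not completed → the stated scoring step not reached → no score of 23 or above to note → self-harm question not required → Mobile Crisis Team step not reached. The parent leaves with interviewer support and a crisis number.

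**2. Would earlier scoring be enough by itself?** Items score 0 to 3 and are summed, so with k items answered the maximum is 3k.
- k = 7: 3 × 7 = 21, below 23.
- k = 8: 3 × 8 = 24, at or above 23.

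At least eight answered items are needed before the trigger can be met, and a parent who has not reached the form has no score. Earlier scoring helps a parent who has filled in the CES-D but not the rest of the packet. It does not help one who stops sooner.

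**3. Do other contacts supply the question?**

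| Provision | Where | What it gives | Self-harm question stated? |
|---|---|---|---|
| Staff available to talk, usually within 24 hours; event documented and reported | Adverse and Unanticipated Events | Conversation, referral, reporting | No |
| Weekly calls for four weeks, both arms | Objectives; Study Design, Procedures and Timeline | Contact, if still enrolled | No |
| Calls at 2 and 4 months, both arms | Study Design, Procedures and Timeline (booster text) | Contact, if still enrolled | No |
| Final phone interview offered on withdrawal; no follow-up afterwards unless the parent is willing to be contacted | Withdrawal of Research Participants | One further contact | No |
| More than two distress referrals prompts a decision on altering the study | Provisions to Monitor the Data | Study-level review | No |

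**4. When is the next scheduled CES-D?** Table 1 places it at enrollment, 6 weeks, 3 months and 6 months.
- After a stopped T1: about 6 weeks, in the online survey.
- After a stopped T3: 6 − 3 = 3 months.
- After a stopped T4: none.

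For a parent who stays enrolled, staff contact comes sooner than the next score: a call about a week after T1, and the 4-month call about 4 − 3 = 1 month after T3.

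**5. Which interview is affected?** The exit interview is outside this point, since it comes last: "Following completion and submission of all questionnaires and the RT journals, participants will be interviewed via speaker phone". Stopping that interview loses no CES-D score.

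**The case against.** The strongest reply is that the plan already handles distress. It provides vigilance, breaks, an offer to stop, support from the interviewer and a route to crisis services. The Mobile Crisis Team belongs to the same county hotline whose number is the alternative to 211, so what differs is who makes the call. Tying suicide assessment to a symptom threshold, and meeting situational upset with support and referral, is a defensible choice. The failure also depends on things not visible here: the order of the forms and what the interviewer's support includes. All of this stands and limits the weight of the point. It does not remove the gap: an interviewer may ask about self-harm, but nothing requires it, and no other contact states the question.

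A reader might infer more than the text supports:
- *That a finished CES-D goes unscored after a stop.* The scoring sentence describes the normal sequence and does not forbid this. If the CES-D comes early in the packet, ordinary good conduct would close much of the gap.
- *That the parent is unseen until the next CES-D, or that withdrawal ends all contact.* The study calls in both arms and the withdrawal phone interview contradict this. Stopping a session is also not the same as withdrawing.
- *That the rate can be gauged from the Background figure of 39.2% of 103 mothers scoring 16 or more in an earlier study.* That figure describes symptom levels at a lower cutoff. It says nothing about how often, or when, sessions are stopped.

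**Conclusion.** The gap is real but narrow. Followed as written, the plan does not require the self-harm question for a parent who stops a T1, T3 or T4 session in distress before a scoreable CES-D exists. The plan itself foresees such distress.

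The size of the problem cannot be put as a probability: the documents give no stop rate, no timing of stops and no form order. The conclusion rests on reading the score of 23 or above as the only stated trigger, which both sections support, and on the absence of a self-harm question from every other contact described. It does not assume that interviewers would fail to ask, or that parents leave without help.

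The effect on trial results is negligible. This is a cheap safety improvement of low-to-moderate priority.

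**What to change.** Two short additions:

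1. In Study Design, Procedures and Timeline (item 2) and in Risks to Research Participants (item 1): whenever a face-to-face session is stopped for distress, the interviewer asks the existing self-harm question whatever the CES-D status, and a positive answer leads to the existing Mobile Crisis Team step.
2. At the scoring sentence in Study Design, Procedures and Timeline: any filled-in CES-D is scored, and the existing steps for above 16 and for 23 or above are applied, before the parent leaves, even if the rest of the packet is unfinished.

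The first addition covers a parent who has not reached the CES-D; the second covers one who has. Cutoffs, forms and form order stay as they are, and both arms are treated alike.

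The cost is a minute or two of interviewer time and one sensitive question to an already upset parent per stopped session. There will also be some additional crisis-team calls, because a positive answer to any part of the question obliges one. Finished sessions need no extra work, since the CES-D is scored there anyway.
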